The Big Health team will send the research team information on the number and date of completed Sleepio sessions for each participant (linked to their access code) as well as completed sleep diaries during the treatment. This information will be sent in an encrypted, password-protected spreadsheet and will not include any personally identifiable information. This will be made clear to participants in the PIS.

Data sharing

For increased reproducibility we aim to publish a fully anonymised data set in an open repository after the study has been completed and main results reported. We will make this clear in the PIS and ask participants to consent to this use of their research data.

Statistical analysis

In accordance with Consolidated Standards of Reporting Trials (CONSORT) guidelines, we will record and report all participant flow (Moher 2010) in addition to providing descriptive statistics of recruitment, dropout, and completeness of interventions. The main efficacy analysis will be conducted on an intentionto-treat basis including all participants. Baseline characteristics will be presented by randomization. We will then test the hypothesis for between-group change in the primary and secondary outcomes at 5 weeks and 10 weeks using analysis of covariance with baseline outcome measure and treatment assignment as fixed effects, and apply standard regression diagnostics. The analysis will use statistical techniques for handling missing outcome data under a missing-at random assumption. If the efficacy analysis shows significant between-group differences in the subjective and objective emotion processing measures at 5 and 10 weeks, modern causal inference methods will be to investigate the mediation hypotheses. Parametric regression models will be employed to test for the indirect effect of emotion regulation/processing at week 5 on depression severity (PHQ-9) at 10 weeks. Since all the measures are continuous, the indirect effects are calculated by multiplying relevant pathways and bootstrapping is used to produce valid standard errors for the indirect effects. All analyses will adjust for baseline measures of the mediators, outcomes and putative measured confounders. Mediation analyses are potentially biased by measurement error in mediators and hidden confounding between mediators and outcomes and we will investigate the sensitivity of the estimates to these problems.

Dissemination

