The main efficacy analysis will be conducted on a modified intention-to-treat basis including all participants having at least one outcome. The primary analyses (emotional processing of faces) differences between treatment groups (dCBT-I and SHE), will be estimated with mixed linear regression models. The main objective of the statistical analyses is to assess the effect of dCBT-I on the primary outcome at the end of the intervention period, 10 weeks. To this end a linear mixed modelling will be employed. In such models, the continuous outcome variable measured at the post randomisation time points features as the dependent, the baseline value of the outcome, stratification factors (sex, age, depression severity and insomnia severity), treatment arm (dCBT-I or SHE), assessment time (5 or 10 weeks) and a treatment x time interaction term included as covariates. To account for correlation between repeated measures on the same individual a subject-varying random intercept will be included. Time will be considered as a categorical variable and model fitted assessed for inclusion of a random slope. Model assumptions will be checked using diagnostic plots. Modelling will be based on the assumption that data are missing at random and will be fitted using restricted maximum likelihood estimation. Results from all analyses will be summarised at 5 and 10 weeks with 2 sided 97.5 % CIs and we will present the data from both adjusted (including stratification variables) and unadjusted models. The adjusted model will be considered the primary analysis.

Handling missing data

The analysis will use statistical techniques for handling missing outcome data under a missing-at random assumption (MAR). The availability of the outcome data for the primary outcome at 10 weeks will be summarised by randomised group.

The mixed effects model implicitly accounts for data missing at random, however the data missingness mechanism will be explored. Logistic regression models will explore any association between baseline characteristics and availability of the primary outcome at 10 weeks. Missing primary outcome data will be reported overall and by randomised group. Covariates found to be predictive of missingness (P< 0.05) will be included in the analysis model in a sensitivity analysis of the primary outcome.

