If post randomisation variables, such as compliance with treatment, or baseline variables are found to be predictive of non-completion of outcome, such that it would not be suitable to adjust for them in the main analyses, then multiple imputation will be considered.

Handling outliers

Any outliers will be checked and verified to ensure that they are true values. Outliers will be identified as those observations more than four standard deviations from the mean. Once they have been confirmed, a sensitivity analysis will be carried out to assess the impact of these values on the results by excluding these participants (see below).

Multiple comparisons and multiplicity

The primary outcome is clearly stated in the protocol. Due to the use of 2 primary outcomes (accuracy for sad and happy faces, respectively) 0.05/2 = 0.025 will be considered significant for the main analysis.

Model assumptions

Standard residual diagnostics, such as inspection of the histogram of the residuals, will be used to assess the appropriateness of the model. If assumptions are violated we will consider firstly using the change in accuracy from baseline as the dependent variable. If the assumptions are still violated we will consider alternative non- parametric approaches.

Secondary analysis

Secondary outcomes

Continuous secondary outcomes will be analysed in the same way as the primary outcome. We will test the hypothesis for between-group difference in the outcomes at 5 weeks and 10 weeks using mixed effects models with baseline outcome measure, treatment assignment, assessment time, stratification variables and a treatment by time interaction as fixed effects with a subject-varying random intercept. We will apply standard regression diagnostics. The proposed analysis assumes that these secondary outcomes are continuous and satisfy the assumptions of the mixed effects model. Where these assumptions are not satisfied, the data will be transformed or if a transformation is not possible, a non-parametric approach to analysing the data will be adopted.

The secondary outcomes include:

Self-rated

The Difficulties in Emotion Regulation Scale (DERS), total score

The Patient Health Questionnaire (PHQ9)

The Penn State Worry Questionnaire PSWQ-Past Week (The PSWQ-PW)

The Perseverative Thinking Questionnaire (PTQ)

Insomnia Severity Index (ISI)

Mood Instability (one self-rated item from the Structured Clinical Interview for DSM-IV (SCID-II))

Munich Chronotype Questionnaire (MCTQ)

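### The SAP's mixed models force one baseline slope on weeks 5 and 10; adding baseline × time is a free safeguard against a small week-10 bias that arises only if the slopes differ and baseline-related dropout differs between arms

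*Combined protocol and SAP*

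**What the plan says.** SAP, Primary analysis (Primary outcome). The purpose is to "assess the effect of dCBT-I on the primary outcome at the end of the intervention period, 10 weeks". The fixed effects are "the baseline value of the outcome, stratification factors (sex, age, depression severity and insomnia severity), treatment arm (dCBT-I or SHE"), followed by "assessment time (5 or 10 weeks) and a treatment x time interaction term included as covariates". For the covariance, "a subject-varying random intercept will be included". On coding, "Time will be considered as a categorical variable and model fitted assessed for inclusion of a random slope". On estimation, "Modelling will be based on the assumption that data are missing at random and will be fitted using restricted maximum likelihood estimation".

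SAP, Secondary analysis (Secondary outcomes). The list is the same: "baseline outcome measure, treatment assignment, assessment time, stratification variables and a treatment by time interaction as fixed effects".

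Protocol, Statistical analysis. Outcomes are compared "at 5 weeks and 10 weeks using analysis of covariance with baseline outcome measure and treatment assignment as fixed effects". The most natural reading is one ANCOVA per visit, each with its own baseline slope, although the protocol does not say so.

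Neither SAP list contains a baseline × time term.

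**The concern.** Treatment × time lets the arm difference vary between visits. Nothing lets the baseline slope vary. If the true slope is lower at week 10 than at week 5, the fitted slope lies between the two: too shallow for week 5, and too steep for week 10, the primary time point. Any baseline imbalance among the participants seen at week 10 is then over-corrected.

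The model's protection under missing at random also requires the mean at each visit to be correct given baseline. A misspecified slope can therefore turn baseline-related dropout into error in the week-10 contrast, even though baseline is in the model. The same form is used for both co-primary outcomes and for every continuous secondary outcome.

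Other provisions in the SAP do not free the slope as written:
- The possible random slope is a between-subject variance term, not a visit-specific effect of baseline.
- The missingness sensitivity analysis adds predictors of missingness as covariates, and baseline FERT accuracy is already one.
- Multiple imputation is only to be considered.
- Residual histograms are unlikely to show a slope that changes by visit.

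**Working it through.** **1. The plan's own figure.** SAP, Sample size calculation: N = 200, 15% loss, effect 0.5 SD. Per arm, 100 × 0.85 = 85. Noncentrality = 0.5 × √(85/2) = 3.260. Power at two-sided α = 0.05 is Φ(3.260 − 1.960) = 90.3%; at α = 0.025 it is Φ(3.260 − 2.241) = 84.6%. The stated 90% and 85% reproduce, and this point does not affect them.

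**2. Mechanism.** Let the true slopes be b5 and b10 (outcomes and baseline in SD units). When both visits are seen, the random-intercept model fits a common slope of about (b5 + b10)/2. The excess at week 10 is e = (b5 − b10)/2. Let Δ be the between-arm difference in mean baseline among those seen at week 10. The error in the week-10 contrast is about e × Δ in absolute size. It is multiplied by about (1 + ρ) if dropouts are still seen at week 5, where ρ is the residual correlation between visits. If the slopes are equal, e = 0. If dropout depends on baseline identically in both arms, Δ = 0 on average. Either one removes the bias.

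**3. Worked case.** Assume b5 = 0.6, b10 = 0.4, ρ = 0.5, 15% dropout and log-odds of dropout of 1 per SD of baseline.
- e = (0.6 − 0.4)/2 = 0.1.
- With X the baseline and p(X) the dropout probability, completers' mean baseline shifts by E[X·p(X)]/0.85 = 0.113/0.85 = 0.133 SD in an arm (numerical integration over a standard normal baseline).
- Opposite directions by arm: Δ = 2 × 0.133 = 0.265, so bias ≈ 0.1 × 0.265 × 1.5 = 0.040 SD.
- One arm only: half of that, 0.020 SD.

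**4. Simulations.** N = 200, 1:1, REML random-intercept fit, 3,000 trials per scenario. Stratification factors were left out of Set B. Entries are the bias of the week-10 effect in SD under the SAP model.

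Set A: correlations (baseline–week 5, baseline–week 10, week 5–week 10) of (0.7, 0.5, 0.6) or (0.7, 0.4, 0.5). Week-10 dropout logit is −2 ± 1 × baseline, with 12–16% missing, half of them seen at week 5. Set B: the assumptions of step 3, with dropouts seen at week 5.

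| Dropout at week 10 | Set A | Set B |
|---|---|---|
| None, or unrelated to baseline | about 0.00 | 0.004 |
| Depends on baseline, same in both arms | −0.004 / 0.000 | 0.003 |
| Same log-odds, different rates by arm | not run | 0.018 |
| Depends on baseline in one arm only | 0.013 / 0.023 | 0.023 |
| Opposite directions by arm | 0.035 / 0.054 | 0.045 |

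Monte Carlo SE in Set B is 0.0024–0.0028. A repeat of Set A with 1,500 trials gave −0.003 and −0.002 (same in both arms), about 0.02–0.03 (one arm) and 0.03–0.055 (opposite). With baseline × time added, the bias is within about 0.006 SD of zero in every run. Equal slopes (0.5/0.5) with opposite-direction dropout give 0.003, that is, none.

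**5. Size against the 0.5 SD target (Set A).** One arm: 0.013/0.5 = 3% to 0.023/0.5 = 5%. Opposite directions: 0.035/0.5 = 7% to 0.054/0.5 = 11%.

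**6. Precision.** In Set B with the same dropout in both arms, the empirical SD of the estimate is 0.140 without the term and 0.138 with it (0.140/0.138 = 1.014). In Set A the difference is about 1%.

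**7. Stress runs (Set B, opposite directions).** Log-odds 2: 0.069. Slopes 0.7/0.3: 0.083. Slopes 0.7/0.3 with 20% dropout and log-odds 2: 0.171.

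**The case against.** The best defence is that bias needs two conditions together, and the documents establish neither. They give no baseline-to-follow-up correlation, and they do not say that dropout depends on baseline FERT accuracy, still less that it does so differently by arm. This stands, and it limits the point to a refinement.

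A reader might infer that any dropout related to baseline biases the primary result. The documents do not support that, and the arithmetic contradicts it: with the same mechanism in both arms, baseline stays balanced among week-10 completers and the error cancels.

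The larger figures also rest on a demanding scenario, in which good recognisers leave one arm and poor recognisers the other, each at an odds ratio of about 2.7 per SD. With one-arm dependence at half that log-odds the bias is 0.004–0.012 SD, under a tenth of the estimate's sampling SD of 0.13–0.14.

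The term also changes inference little. Simulated coverage of the 97.5% interval moves from 96.1% to 96.4% and from 94.6% to 95.2% (one arm, two correlation sets), and from 94.6% to 95.6% and 94.1% to 95.4% (opposite directions). It does not restore nominal coverage.

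A reader might also see a contradiction between the protocol's ANCOVA and the SAP's joint model. The protocol never promises visit-specific slopes, so there is nothing to reconcile.

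On the other side, arm-differential dropout is plausible. Participants know their allocation, and the burden differs: six sessions with daily diaries against a website of advice. The SAP's missingness regression could reveal baseline-related dropout, but no planned analysis would then free the slope.

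**Conclusion.** The restriction is real: both mixed models impose one baseline slope on weeks 5 and 10. If baseline predicts week 10 less well than week 5, the cost is about 1–2% in standard error. There is bias in the week-10 effect only if baseline-related dropout also differs between arms.

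Under assumed correlations of 0.7 at week 5 and 0.4–0.5 at week 10, that bias is about 0.01–0.03 SD with dependence in one arm and up to about 0.055 SD in the extreme opposite-direction case, against a 0.5 SD target. It is nil with equal slopes. Its sign depends on which arm loses which participants, which cannot be known in advance. Steeper fading with stronger and more frequent dropout gives larger values, but these are stress tests with no basis in the documents. The documents do not show that the planned analysis is biased. The case for the change is that it removes the exposure at almost no cost.

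**What to change.** In the SAP, add a baseline-outcome × time interaction to the fixed effects of the model under Primary analysis (Primary outcome) and of the model under Secondary analysis (Secondary outcomes). Keep treatment × time, the stratification factors and all other terms as planned, and report the week-10 contrast from that model. Specify it in advance, so that the choice does not depend on the data.

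Cost: one fixed-effect parameter per model and a few words of SAP text. It needs no new data and no change to the sample size. If the slopes are equal, essentially nothing is lost: in Set B with slopes 0.5/0.5, the empirical SD is 0.1337 with the term and 0.1326 without.

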Appendix 5k)			
ECAT	X	X	X
EMEM	X	X	X
Audit of engagement		Х	Х
with mental health			
services and sleep			
medication			
(Appendix 5i)			
Device Monitoring	X	X	X
Question(s)			
(Appendix 5a)			

Fig 2: Standard Protocol Items: Recommendations for Interventional Trials (SPIRIT) figure.

Randomisation and allocation concealment

Randomization will be performed independently from the study team through the ePRO system. This study will use stratified randomisation with an allocation ratio of 1:1, as recommended for small scale clinical trials (Kernan et al., 1999). Randomisation and stratification according to sex (male/female), age (25-44, 45-65), depression severity (PHQ-9 Scores: $\leq 15: \geq 16$) and insomnia severity (ISI scores $\leq 19: \geq 20$). On completion of baseline measures each participant will be randomly assigned to either dCBT-I or SHE. The team will be unable to influence randomization in the ePRO system, but will manually contact the participant to inform them of their allocation.

Blinding and bias

Self-report assessments and performance tasks will be completed entirely online. Participants will be informed of their randomisation outcome (dCBT-I or SHE, referred to as sleep treatment 1 and 2 in the PIS) and will not be blind to treatment allocation. To minimise bias, the PIS will not explicitly reveal that SHE is used as a minimal control.

End of study

The end of study is defined as the last participants completed the last assessment (10 weeks).

Sample size calculation

Our planned primary intention-to-treat analysis will compare dCBT-I versus SHE for objective biases in negative emotional processing of faces at week 10. Our desired sample size of n=200 and an estimated attrition rate of 20% (based on recently completed trials (Kyle et al., 2017)), will be powered to detect a minimum between group standardized effect size of 0.5 at week 10, with a power of 90% and a two-tailed α of 0.05.

Recruitment and payment

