Sample size calculation

Our planned primary intention-to-treat analysis will compare dCBT-I versus SHE for objective biases in negative emotional processing of faces at week 10. Our desired sample size of n=200 and an estimated attrition rate of 15% (based on recently completed trials (Kyle et al., 2017)), was powered to detect a minimum between group standardized effect size of 0.5 at week 10, with a power of 90% and a two-tailed α of 0.05.

Considering the co-primary outcome, alpha will be adjusted to 0.025 to control the overall type 1 error rate. Therefore, conservatively assuming an alpha of 0.025 and no correlation between the outcomes; the study would be able to detect an effect size of 0.5 with 85% power on the two primary outcomes (recognition accuracy in response to happy and sad facial expressions). The sample size remains inflated to allow for a rate of by 15% lost to follow up.

Adverse events

Since the trial is completed online, with limited formal participant contact, we are unlikely to become aware of all potential adverse events. However, should we do so, we will define serious adverse events as: (1) death, (2) suicide attempt, and (3) admissions to secure units.

[figure not shown]
Analysis – general considerations

Statistical software

Analyses and processing of the data will be performed in R (R Core Team (2020). R: A language and environment for statistical computing. R Foundation for Statistical Computing, Vienna, Austria. https://www.R-project.org/). Mixed effect models will be run using the lme4 and nlme packages, CACE analyses will be performed using the eefAnalytics package and mediation analyses will be performed using the MEDIATION package.

Descriptive statistics

We will present the data using a CONSORT diagram, see figure below.

Frequencies (with percentages) for binary and categorical variables and means (and standard deviations), or medians (with lower and upper quartiles) for continuous variables will be presented by intervention group as well as overall.

Characteristics of participants

Baseline variables will be presented by randomised group using frequencies (with percentages) for binary and categorical variables and means (and standard deviations) or medians (with lower and upper

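### Two contingency steps in the primary model do not do their job: the change-score remedy leaves the residuals unchanged while baseline stays a covariate, and a random slope cannot be assessed with two outcome visits

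*Combined protocol and SAP*

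**What the plan says.** The SAP's Primary analysis section models the post-randomisation values of FERT accuracy at weeks 5 and 10. The covariates are baseline accuracy, the stratification factors, treatment, visit and treatment by visit. On the covariance it says: "To account for correlation between repeated measures on the same individual a subject-varying random intercept will be included". It continues: "Time will be considered as a categorical variable and model fitted assessed for inclusion of a random slope".

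Under Model assumptions, residual plots are inspected, and then: "If assumptions are violated we will consider firstly using the change in accuracy from baseline as the dependent variable". If that does not help, non-parametric methods are to be considered, but none is named. Nothing says that baseline leaves the covariate list when the dependent variable changes. The Secondary outcomes section offers a transformation step; the primary outcome has none.

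The two co-primary outcomes, accuracy for sad and for happy faces, are percentages of faces correctly identified. For each, "0.05/2 = 0.025 will be considered significant for the main analysis". The Statistical software section names both lme4 and nlme for the mixed models.

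**The concern.** Each step is meant to protect the confirmatory analysis, and neither does so as written.

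- **Change score.** Subtracting a variable that is already a regressor cannot alter the residuals. A diagnostic that fails before the step fails identically after it, and the analysis passes straight to an unnamed non-parametric method. The primary outcome is bounded at 0 and 100%, so skewed residuals are plausible, and the replacement method would be chosen after seeing the data.
- **Random slope.** With two outcome visits, the usual correlated intercept-and-slope model has more variance parameters than the data can determine. What happens next depends on which named package is used. If the analyst falls back to the random intercept alone, the week-10 standard error uses a variance pooled over both visits. It is then too small if week 10 is more variable than week 5, and too large in the opposite case. The 0.025 threshold for each co-primary outcome relies on that standard error.

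**Working it through.** **The plan's own figures.** The SAP gives N = 200, 15% attrition, effect size 0.5 and 1:1 allocation.
- Per arm at α = 0.05 and 90% power: 2(1.960 + 1.282)²/0.5² = 84.1, so 85. Then 170/0.85 = 200.
- Power at α = 0.025: Φ(0.5·√(85/2) − 2.241) = Φ(1.018) = 84.6%. The SAP says "the study would be able to detect an effect size of 0.5 with 85% power on the two primary outcomes".
- Power at α = 0.05: Φ(3.260 − 1.960) = 90.3%, against the stated 90%.

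Both figures reproduce, and nothing below changes them.

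**Change score.** Write the model as Y = Xβ + γB + u + e, with B the baseline accuracy. Then Y − B = Xβ + (γ − 1)B + u + e. Only the coefficient of B moves, by exactly 1.

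This was checked on one simulated data set. Its settings are assumptions, because the documents give neither the number of faces nor an accuracy SD: 200 participants, 20 faces per emotion, about 15% missing per visit.

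| Fit (REML) | Baseline coefficient | Week-10 effect (SE) | Log-likelihood |
|---|---|---|---|
| Raw score | 0.627 | 3.200 (1.631) | −1322.5217 |
| Change, baseline kept | −0.373 | 3.200 (1.631) | −1322.5217 |
| Change, baseline dropped | – | 3.63 (1.81) | – |

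The largest residual difference between the first two fits is about 3×10⁻¹², which is rounding. With baseline dropped, residuals move by up to 11.5 points and skew goes from −0.70 to −0.19, but the SE rises from 1.63 to 1.81.

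**Random slope.** Code the visits 0 and 1. Let g11, g22 and g12 be the intercept variance, slope variance and their covariance, and s² the residual variance.
- Var(week 5) = g11 + s²
- Cov = g11 + g12
- Var(week 10) = g11 + 2·g12 + g22 + s²

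That is three equations for four unknowns. The Jacobian rank is 3 of 4 under 0/1, 5/10 and centred coding. For example, variances 150 and 170 with covariance 90 are reproduced exactly by (g11, g12, g22, s²) = (140, −50, 120, 10), (110, −20, 60, 40) and (90, 0, 20, 60).

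On the simulated data:
- The REML log-likelihood, profiled over s², is flat: −1004.5404 (up to a constant) at s² = 5, 15, 25 and 35. The week-10 effect is 3.214 at each value.
- lme4 stops by default, because 352 observations do not exceed 394 random effects (2 × 197 participants). With at most two observations and exactly two random effects per participant, this must always occur.
- nlme returns a fit, but its split between slope and residual variance is arbitrary.

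**If only the random intercept remains.** With complete data, the week-10 SE uses the average of the two visit variances. The large-sample type I error at nominal 2.5% is 2[1 − Φ(2.241·√(pooled variance / week-10 variance))]. The SD ratios are assumptions.

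| Assumed SDs (week 5 : week 10) | Pooled variance | Variance ratio | Adjusted z | Type I error |
|---|---|---|---|---|
| 1 : 1.2 | (1 + 1.44)/2 = 1.22 | 1.22/1.44 = 0.847 | 2.063 | 3.9% |
| 1 : 1.3 | (1 + 1.69)/2 = 1.345 | 1.345/1.69 = 0.796 | 2.000 | 4.6% |
| 1.2 : 1 | 1.22 | 1.22 | 2.476 | 1.3% |

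Simulations at 85 per arm scatter around these values: 3.5–4.0%, 4.4–4.9% and 1.3–1.5% respectively. Using visit-specific variances kept the error at 2.4–2.7%.

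**The case against.** The strongest replies, and what stands of each:

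- **The slope rule still has a use.** A reader might infer that it cannot be run at all, or that it invalidates the week-10 result. The documents do not support that. Only the split between slope and residual variance is undetermined; the 2×2 marginal covariance and the week-10 effect remain identified. Any positive-definite 2×2 matrix can be written as intercept, slope and residual parts, so an nlme fit with the slope is in effect an unstructured covariance. Assessing the slope there amounts to testing whether the two visit variances differ. An uncorrelated slope is also just identified under 0/1 or 5/10 coding, though not under centred coding. This stands, but the SAP specifies neither route, and the other named package stops by default.
- **The inflated error rates are conditional.** A reader might infer that the trial will run at 4–5% error per outcome. The documents give no FERT SD at any visit, so the ratios are assumed, and the rates arise only if equal variance is retained. Diagnostic plots might also reveal unequal spread. This stands.
- **Baseline may have been meant to leave the model.** The wording changes only the dependent variable, so keeping baseline is the natural reading. If it is dropped, the step is no longer empty, but it generally costs precision. Either way the text needs correcting.
- **Skewed residuals may do little harm.** Simulations with an assumed 20 faces and typical accuracy of 80%, 90% and 95% gave type I error of 2.7%, 2.4% and 2.4% at nominal 2.5%. The inference that a ceiling breaks the primary test is therefore not supported. The point is that the stated remedy is empty.
- **A binomial mixed model is not a like-for-like substitute.** It yields an odds ratio, whereas the SAP powers a standardised mean difference. This stands and shapes the fix.

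**Conclusion.** The concern holds in limited form. With baseline retained, the change-score step does nothing; this is algebra and needs no assumption about the data. The random slope cannot be assessed as a variance component in the usual correlated form, because two visits give three moments for four parameters. Neither defect biases the week-10 estimate.

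The risk to inference is conditional. It needs the model to end at a random intercept and the visit variances to differ. Under the assumed ratios, type I error at nominal 2.5% is then about 3.9–4.0% (week-10 SD 20% larger), 4.6–4.9% (30% larger) or 1.3–1.5% (week-5 SD 20% larger). Single simulations fell as low as 3.5% and 4.4% in the first two cases. The closed form does not depend on the number per arm. The change is worth making because these are stated rules that fail at their purpose, and correcting them is nearly free.

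**What to change.** 1. **Covariance.** Replace the random intercept and the slope assessment with a prespecified unstructured 2×2 residual covariance by visit, fitted by REML with `gls` in nlme using `corSymm` and `varIdent`. This has three covariance parameters against two for the random intercept, so it costs one extra variance parameter. nlme is already named.
2. **Failed assumptions.** Delete the change-score step. Name a remedy that keeps the mean difference in percentage accuracy as the estimand, such as bootstrap or robust standard errors, with baseline kept as a covariate. If a non-parametric step is retained after that, name the method.
3. **Bounded outcome.** A binomial mixed model on correct/total counts can be added as a sensitivity analysis.

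The cost is SAP wording and a few lines of code. No new data are needed, and the sample size and the stated 85% and 90% power are unaffected.
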